4.0 TREATMENT PLAN

4.1 Overview

Patients will take oral pazopanib (800mg starting dose) once daily AND oral toptecan (8 mg starting dose) on days 1, 8, and 15 of each 28 day cycle. Treatment will continue until disease progression or unacceptable toxicity occurs, or until discontinuation per patient preference or physician recommendation. Patients who are removed from study treatment for toxicity should be followed until toxicity resolves to grade 1 or baseline. Patients **with PD** at end of treatment will be followed every 6 months for 2 years (or until death) for survival. Patients **without PD** at end of treatment will be followed every 6 months for 5 years (or until death) for survival and progression.

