4.3 Toxicity Management, Dose Delays/Modifications & Supportive care

Any patient who receives at least one dose of study therapy will be evaluable for toxicity endpoints. Each patient will be assessed for the development of toxicity according to the timeframe referenced in the Schedule of Events table). Toxicity will be assessed according to CTCAE v. 4.03.

After cycle 1 day 1 of therapy, defined as 4 weeks of therapy, cycle 1 day 15, cycle 2 day 1, cycle 2 day 15, cycle 3 day 1, and day one of all subsequent cycles may be administered provided the patient meets the following criteria:

- ANC \geq 1500/mm²
- Platelet count \geq 75,000
- Hemoglobin \geq 9 g/dL (after transfusion if necessary).
- Non-hematologic toxicity recovered to \leq grade 1 or tolerable grade 2
- No evidence of progressive disease

Note: For cycle 1 day 15 and cycle 2 day 15, dosing should only commence AFTER day 15 labs have been reviewed to ensure the above criteria are met. If the patient does not meet the above criteria, study treatment should be held and labs and assessment should be done at least weekly until patient meets the above criteria (patient can be assessed earlier than one week at physician's discretion). If when reassessed, the patient meets the treatment criteria above, proceed with treatment at the dose the patient was receiving during the previous cycle. If patient does not meet the above criteria after a one-week delay, then treatment will continue to be held, and the patient will continue to be evaluated weekly. Treatment can be held for a total of 3 consecutive weeks to allow for treatment related toxicities to resolve. In the case that treatment has been held for 3 weeks for treatment related toxicities, the dose reduction for the next upcoming cycle should be based on the most severe toxicity experienced in the current cycle. If a patient develops another severe toxicity at the reduced dose or if they experience a life-threatening toxicity at any time, they will be removed from study per the dose modification parameters below. If a subject is able to resume treatment after an interruption of \leq 3 weeks, missed doses will not be made up (i.e. the cycle duration will remain unchanged).

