Patients with stable or responding disease may be retreated at the same dose (both Topotecan and Pazopanib) or at a reduced dose level, depending upon the adverse events observed in the current cycle and any adverse events present on the first day of the next cycle. If multiple toxicities are seen, the dose administered in a subsequent cycle should be based on the most severe toxicity experienced in the current cycle. Any doses that are held or delayed will be considered skipped and will not be made up. Patients should not deviate from the 28 day cycle (+ or – 3 days).

Patients will be withdrawn from the study if they fail to recover to grade \leq 1 or tolerable grade 2 (or within 1 grade of starting values for pre-existing laboratory abnormalities) from a treatment-related toxicity within 3 weeks, or if the dose is interrupted $>$ 8 weeks for a non-treatment related reason, unless the investigators (PI, local PI, and QAM) agree that the subject should remain in the study because of evidence that the patient is/may continue to derive benefit from continuing study treatment.

Topotecan:

Three dose reductions are permitted, based on side effects experienced, from 8 mg to 6, 6mg to 4, 4mg to 2. Further dose reduction is not allowed. Patients may be maintained on the lower dose of topotecan during treatment if deemed to be deriving benefit from the drug. Doses that are reduced for topotecan related toxicity will not be re-escalated, even if there is minimal or no toxicity with the reduced dose.

| | |
|-------------------|-----------|
| Dose Level | Topotecan |
| 0 (starting dose) | 8 mg |
| -1 | 6 mg |
| -2 | 4 mg |
| -3 | 2 mg |

Pazopanib:

Pazopanib may be held up to 3 weeks waiting for toxicities to resolve. Three dose reductions are permitted, from 800 to 600 or from 600 to 400 or from 400 to 200 mg daily based on side effects experienced. Further dose reduction is not allowed. Patients may be maintained on the lower dose of pazopanib during treatment if deemed to be deriving benefit from the drug. Doses that are reduced for pazopanib related toxicity will not be re-escalated, even if there is minimal or no toxicity with the reduced dose.

| Table I- Dose Modification Algorithms for Potential Treatment-Related Adverse Events^c | |
|--|--|
| AE Terms & Descriptions | Dose Modification Algorithms |
| Hypertension | |

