| Neutrophils $<$ 1.5 | 
1. Interrupt pazopanib and topotecan dosing until neutrophils resolve to \geq 1.5.
 
2. Restart topotecan and pazopanib at the current dose or reduce dose by 1 level per physician discretion.
 
If no recovery to \geq 1.5 within 3 weeks, discontinue protocol treatment and follow-up per protocol. If patient is deriving clinical benefit, please contact QAM and PI.
 |
| Anemia: Investigate and document underlying cause. | |
| Hemoglobin \geq 9 | Continue pazopanib and topotecan at current dose; monitor as clinically indicated. |
| Hemoglobin $<$ 9 | 
1. Interrupt pazopanib and topotecan dosing until hemoglobin resolves to \geq 9.
 
2. Restart topotecan and pazopanib at the current dose or reduce dose by 1 level per physician discretion.
 
If no recovery to \geq 9 within 3 weeks, discontinue protocol treatment and follow-up per protocol. If patient is deriving clinical benefit, please contact QAM and PI.
 |
| Palmar-plantar Erythrodysesthesia Syndrome | |
| Grade 1 Minimal skin changes or dermatitis without pain (erythema, oedema, hyperkeratosis) | 1. Continue pazopanib and topotecan at present dose |
| Grade 2 Skin changes with pain; limiting instrumental activities of daily living (ADLs) (peeling, blisters, oedema, bleed, hyperkeratosis) | 
1. Hold pazopanib. Continue topotecan at current dose.
 
2. Treat as clinically appropriate
 
3. Upon resolution to Level 1 or better restart pazopanib with a dose reduction to 400 mg
 
4. If recurrent at the current dose consider a further dose reduction to 200mg or discontinuation
 |
| Grade 3 Severe skin changes with pain and limiting self care ADLs | 1. Discontinue protocol treatment |

| Other Treatment Related Adverse Events^{b,c,d} | |
|---|--|
| Grade 1 or tolerable Grade 2 | Continue pazopanib and topotecan at current dose; monitor as clinically indicated. |
| Intolerable Grade 2 or Grade 3 | Step 1. Interrupt pazopanib and topotecan until toxicity resolves to ≤ Grade 1. Step 2. Restart topotecan and pazopanib at the current dose or reduce dose by 1 level per physician discretion. |
| Grade 4 | Discontinue protocol treatment and continue follow-up per protocol. |

- a. Well-controlled BP defined as SBP <140 mmHg and mean DBP <90 mmHg.
- b. AEs are graded according to NCI Common Terminology Criteria for Adverse Events v4.0 (NCI CTCAE v4.03)
Abbreviations: BP, blood pressure; IP, investigational product.

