4.4.1 G-CSF Administration

If neutrophil count < 1500/mm³ or platelet count < 75,000/mm³, hold topotecan until counts resolve to < grade 2 CTC grade toxicity. If neutrophil count remains < 1500/mm³ x 1 week or more, granulocyte colony stimulating factor may be used to support. If neutrophil count achieves level > 1500/mm³, patient may resume treatment with oral topotecan. If toxicities do not resolve to < CTC grade 2 after 3 weeks of drug hold, and with G-CSF support patient must be removed from study. Platelet counts that do not resolve to < CTC grade 2 after 3 weeks require removal of patient from treatment.

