If a patient is felt to be deriving benefit from the agents and is stable at the conclusion of the trial, patients are allowed to continue therapy with stable disease by RECIST 1.1. This will be based on discussion with the patient, the PI, and sponsor. It may be possible to continue both drugs at that point, assuming availability of agents and no change in the status regarding pazopanib or topotecan with respect to sarcomas.

A patient may be removed from therapy if, in the judgment of the investigator, general or specific changes in the patient's condition render the patient unacceptable for further treatment.

4.6 **Duration of Follow Up**

Patients with PD at end of treatment will be followed every 6 months for 2 years (or until death) for survival. Patients without PD at end of treatment will be followed every 6 months for 5 years (or until death) for survival and progression. Follow-up may occur over the phone. Patients who are removed from study treatment for toxicity should be followed until toxicity resolves to grade 1 or baseline.

4.7 **Removal of Subjects from Study Treatment and/or Study as a Whole**

Patients can be taken off the study treatment and/or study as a whole at any time at their own request, or they may be withdrawn at the discretion of the investigator for safety, behavioral or administrative reasons. The reason(s) for discontinuation must be clearly documented on the appropriate eCRF and may include:

- Patient voluntarily withdraws from treatment (follow-up permitted)
- Patient withdraws consent (no follow-up permitted)
- Patient is unable to comply with protocol requirements

- Patient demonstrates disease progression
- Patient experiences unacceptable toxicity
- Treating physician determines that continuation on the study would not be in the patient's best interest
- Patient becomes pregnant
- Patient develops a second malignancy that requires treatment which would interfere with this study
- Patient becomes lost to follow-up (LTF)

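### Sections 4.3 and 4.4.1 take patients off the study for toxicity where Table I and Sections 4.1 and 4.6 stop only treatment, so long-term progression and survival follow-up may be censored because of toxicity

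*Combined protocol and SAP*

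**What the plan says.** The off-study wording appears in three places.

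- Section 4.3, on treatment-related toxicity that has not resolved after three weeks: "Patients will be withdrawn from the study if they fail to recover to grade" 1 or a tolerable grade 2. The exception is that the investigators and the quality assurance monitor may "agree that the subject should remain in the study because of evidence that the patient is/may continue to derive benefit from continuing study treatment".
- Section 4.3, on a further severe toxicity at a reduced dose, or "if they experience a life-threatening toxicity at any time, they will be removed from study per the dose modification parameters below".
- Section 4.4.1, on toxicity that persists after a three-week hold: "with G-CSF support patient must be removed from study". The next sentence, on platelets, speaks of removal from treatment instead.

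Other current text keeps such patients in follow-up.

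- Table I in Section 4.3, for Grade 4 events among the other treatment-related adverse events: "Discontinue protocol treatment and continue follow-up per protocol". The neutropenia, anemia and Grade 2 thrombocytopenia rows give the same outcome in similar words when there is no recovery within three weeks.
- Section 4.1, repeated in 4.6 and in footnote j to the study procedures table: "Patients who are removed from study treatment for toxicity should be followed until toxicity resolves to grade 1 or baseline".
- Sections 4.1 and 4.6 and footnote i: patients without progression at end of treatment are contacted six-monthly for five years for survival and progression. Those with progression are contacted for two years for survival.

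Section 4.7 treats the two statuses as different: "Patients can be taken off the study treatment and/or study as a whole at any time at their own request". Its list of reasons marks voluntary withdrawal from treatment as allowing follow-up and withdrawal of consent as barring it. Unacceptable toxicity is listed with neither label.

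**The concern.** The question is not when treatment stops but what study status the patient has afterwards. A site that applies the 4.3 or 4.4.1 sentence literally would code the patient off study, and one that applies Table I would code the same patient off treatment and keep calling. Eight sites are listed, so both codings could occur.

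Section 10.3 estimates PFR and OS by Kaplan-Meier in each histologic group. That method assumes that a patient censored at a given time has the same later risk as those still followed. If patients leave because of unresolved or life-threatening toxicity, and that toxicity or the treatment stop is related to later progression or death, the assumption fails.

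**Working it through.** No formula in the plan depends on this wording, so the check sets the rules side by side.

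| Trigger | 4.3 text or 4.4.1 | Table I | Same status? |
|---|---|---|---|
| Neutrophils not recovered after three weeks | 4.4.1 (with G-CSF support): off study. 4.3 (if treatment-related): off study | Treatment stopped, follow-up kept | No |
| Hemoglobin not recovered after three weeks | 4.3 (if treatment-related): off study | Treatment stopped, follow-up kept | No |
| Life-threatening toxicity (compared with Grade 4, other treatment-related events) | 4.3: off study, by reference to the dose modification rules | Treatment stopped, follow-up kept | No on the words; the reference leads to the rule that keeps follow-up |
| Platelets not recovered after three weeks | 4.4.1: off treatment. 4.3 (if treatment-related): off study | Treatment stopped, follow-up kept (Grade 2 row) | 4.4.1 yes, 4.3 no |

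1. The clearest clash is neutropenia. One event, still open after three weeks, has two different study statuses in current text.
2. Section 4.7 cannot settle it. It separates the statuses, but its toxicity entry does not choose between them.
3. The exception in 4.3 does not help a patient who has stopped both drugs, because it depends on benefit from continuing treatment.
4. What a literal reading removes: for a patient without progression at end of treatment, 4.6 plans contact every six months for five years, so 5 × 2 = 10 contacts. For a patient with progression it plans 2 × 2 = 4 survival contacts. Off study, these rules would supply none.
5. What other text restores: Section 7.1 requires every patient with an adverse event to be followed to resolution or return to baseline, another satisfactory explanation, or death, with no condition that the patient be on study. It does not cover progression or survival, and no other section restores those.
6. The number of patients taken off study under these sentences is not in the documents, nor is their later course. Neither the size nor the direction of any bias in the Kaplan-Meier curves can be computed.

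**The case against.** The best reply is that the authors meant study treatment and wrote study. Much of the context supports this. The life-threatening toxicity sentence sends the reader to tables that keep follow-up. The 4.3 exception speaks of remaining in the study in order to continue treatment. In 4.4.1 the neighbouring platelet sentence says treatment. In 4.7 only withdrawal of consent expressly bars follow-up, and no sentence says that withdrawal under 4.3 ends it. This makes the intended meaning likely and the life-threatening toxicity sentence the weakest of the three. It does not remove the problem, because a site must infer the intent against the literal words while 4.7 says that the two statuses differ.

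Three stronger readings are tempting, and the documents do not support them.

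- A reader might infer that the course of the worst toxicities goes unrecorded. Section 7.1 largely prevents this. Serious events are also reportable up to 30 days after the last dose, and later events if they are attributed to the drugs.
- A reader might infer that the 12-week primary result is biased. Section 6.3 makes a patient non-evaluable, subject to DMC approval, on removal from treatment before week 12 for reasons other than progression or death. That rule applies whichever way the study status is read. The decision rule is a count out of 92 evaluable patients, and the six-monthly contacts in 4.6 are not designed to supply a week-12 scan.
- A reader might take the 16 extra STS enrolments (108 − 92) as a measure of the problem. They allow for non-evaluable patients, and the documents do not give the causes of non-evaluability.

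**Conclusion.** The inconsistency is real, stands in current operative text and should be corrected. What is exposed is long-term progression and survival follow-up after a toxicity stop, and through it the Kaplan-Meier PFR and OS estimates in all three histologic groups. The exposure is up to ten planned contacts per affected patient without progression; the number of such patients is unknown.

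Informative censoring is a risk and not a demonstrated bias. It rests on two assumptions that the documents cannot confirm: that at least one site coded patients off study under the literal wording, and that these patients' later risk differs from that of patients still followed. Nothing shows a deliberate decision to end follow-up after toxicity, so this is a matter of conflicting terms. No effect on the 12-week decision rule is claimed, and only a limited one on safety follow-up.

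**What to change.** - In Section 4.3 (both sentences) and Section 4.4.1, reconcile the wording with Table I, 4.1 and 4.6. State that these rules concern discontinuation of protocol treatment and that the patient remains in follow-up for toxicity, progression and survival under 4.1 and 4.6 unless consent is withdrawn.
- Make the toxicity entry in 4.7 say the same. Leave the other 4.7 grounds for removal from the study as they are. Limiting study removal to withdrawn consent or loss to follow-up would conflict with the investigator discretion that 4.7 grants.
- Leave every treatment-stopping trigger unchanged. This point proposes no clinical rule.
- Check whether any patient already coded off study for toxicity should still be in follow-up and, where consent allows, resume contact.

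The cost is a few wording edits, one check of off-study codes, and contacts that the protocol already plans and allows by telephone. The amendment history records that accrual is closed, but follow-up can run for five years after treatment, so the clarification may still recover data.

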4.3.1 Pregnancy/Lactation/Contraception

Pre-clinical studies in animals have shown reproductive toxicity. If the patient becomes pregnant while receiving pazopanib or topotecan, the potential hazard to the fetus should be explained to the patient. Women of childbearing potential should be

advised to avoid becoming pregnant while receiving treatment with pazopanib or topotecan. Pazopanib or topotecan should not be used during pregnancy or lactation.

Acceptable contraception methods, when used consistently and in accordance with both the product label and instructions of the physician are as follows:

- Complete abstinence from sexual intercourse during duration and treatment and for at least 30 days after the last dose of investigational product.
- Oral contraceptive, either combined estrogen/progesterone or progesterone alone.
- Injectable progestogen.
- Implants of levonorgestrel.
- Estrogenic vaginal ring.
- Percutaneous contraceptive patches.
- Intrauterine device (IUD) or intrauterine system (IUS) with a documented failure rate of less than 1% per year.
- Male partner sterilization (vasectomy with documentation of azoospermia) prior to the female patient's entry into the study, and this male is the sole partner for that patient.
- Double barrier method: condom and an occlusive cap (diaphragm or cervical/vault caps) with a vaginal spermicidal agent (foam/gel/film/cream/suppository).

4.4 Concomitant Medications/Treatments

Use of concomitant medications for supportive care purposes will be per treating investigator's discretion.

4.4.1 G-CSF Administration

If neutrophil count < 1500/mm³ or platelet count < 75,000/mm³, hold topotecan until counts resolve to < grade 2 CTC grade toxicity. If neutrophil count remains < 1500/mm³ x 1 week or more, granulocyte colony stimulating factor may be used to support. If neutrophil count achieves level > 1500/mm³, patient may resume treatment with oral topotecan. If toxicities do not resolve to < CTC grade 2 after 3 weeks of drug hold, and with G-CSF support patient must be removed from study. Platelet counts that do not resolve to < CTC grade 2 after 3 weeks require removal of patient from treatment.

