| Grade 3 | 
Step 1. Interrupt pazopanib. Continue topotecan at the current dose.
 
Step 2. Initiate and monitor anticoagulation as clinically indicated.
 
Step 3. Resume pazopanib at reduced dose only if all of the following criteria are met:
 
 • The subject must have been treated with anticoagulant at the desired level of anticoagulation for at least one week. • No Grade 3 or 4 or clinically significant Grade 2, hemorrhagic events have occurred while on anticoagulation treatment. 
Subject should be monitored as clinically indicated during anticoagulation treatment and after resuming study treatment. When treating with warfarin, international normalized ratio (INR) should be monitored within three to five days after any change in IP dosing (eg, re-initiating, escalating/de-escalating, or discontinuing IP), and then at least weekly until the INR is stable. The dose of warfarin (or its derivatives) may need to be adjusted to maintain the desired level of anticoagulation
 |
| Grade 4 and/or PE | Discontinue protocol treatment and continue follow-up per protocol. |
| Arterial Thrombosis/Ischemia | |
| Any Grade | Discontinue protocol treatment and continue follow-up per protocol. |
| Thrombocytopenia: Investigate and document underlying cause | |
| Grade 1 | Continue pazopanib and topotecan at current dose; monitor as clinically indicated. |
| Grade 2 | 
Step 1. Interrupt topotecan and pazopanib until toxicity resolves to \leq Grade 1.
 
Step 2. Restart topotecan and pazopanib at the current dose or reduce dose by 1 level per physician discretion.
 
If no recovery to \leq Grade 1 within 3 weeks, discontinue protocol treatment and follow-up per protocol. If patient is deriving clinical benefit, please contact QAM and PI.
 |
| Grade 3 or 4 | Step 1. Interrupt pazopanib and topotecan until toxicity resolves to \leq Grade 1. |

| | |
|---|--|
| | 
Step 2. Restart pazopanib dose-reduced by 200 mg and monitor as clinically indicated. Restart topotecan at the current dose or reduce dose by 1 level per physician discretion.
 
If no recovery to \leq Grade 1 or recurrent Grade 3 or 4 thrombocytopenia at the current dose, discontinue protocol treatment and follow-up per protocol.
 |
| Neutropenia: Investigate and document underlying cause. | |
| Neutrophils \geq 1.5 | Continue pazopanib and topotecan at current dose; monitor as clinically indicated. |

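### Section 4.4.1 is out of line with 4.3 and Table I on cytopenias: it holds topotecan only, removes patients from study rather than treatment, and leaves the benefit exception unsettled at 3 weeks

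*Combined protocol and SAP*

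**What the plan says.** **Section 4.4.1 (G-CSF Administration)** applies when neutrophils are below 1500/mm³ or platelets below 75,000/mm³. Its instruction is to "hold topotecan until counts resolve to < grade 2 CTC grade toxicity". G-CSF may be added after a week of persistent neutropenia, and oral topotecan may resume once neutrophils recover. Pazopanib is not mentioned. If toxicities have not resolved "after 3 weeks of drug hold, and with G-CSF support patient must be removed from study". For platelets: "Platelet counts that do not resolve to < CTC grade 2 after 3 weeks require removal of patient from treatment". Neither sentence has an exception, and the section does not refer to 4.3 or Table I.

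**Section 4.3, general text.** If the blood-count criteria are not met at a dosing checkpoint, "study treatment should be held and labs and assessment should be done at least weekly". A hold for treatment-related toxicity may last 3 consecutive weeks. A patient who has not recovered by then is withdrawn, "unless the investigators (PI, local PI, and QAM) agree that the subject should remain in the study" because of evidence of benefit.

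**Section 4.3, Table I.**
- Grade 2 thrombocytopenia: "Interrupt topotecan and pazopanib until toxicity resolves to" grade 1 or better. If there is no recovery "within 3 weeks, discontinue protocol treatment and follow-up per protocol. If patient is deriving clinical benefit, please contact QAM and PI".
- Neutrophils below 1.5: the same structure. Both drugs are interrupted, with the same stop and the same contact instruction at 3 weeks.
- Grade 3 or 4 thrombocytopenia: both drugs are interrupted. For no recovery or "recurrent Grade 3 or 4 thrombocytopenia at the current dose, discontinue protocol treatment and follow-up per protocol". This row has no contact instruction and no 3-week limit of its own.

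No section says which text governs.

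**The concern.** Two sets of instructions cover the same cytopenias, and a site can reach either one first. Three differences matter.

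1. **Which drug is held.** A site that works from 4.4.1 alone could keep giving pazopanib through a neutropenia or thrombocytopenia for which Table I stops both drugs. It could also restart without Table I's dose rules. For grade 3 or 4 platelets, Table I restarts pazopanib at a dose reduced by 200 mg.
2. **What the patient leaves.** 4.4.1 removes the G-CSF-supported patient from the study. Table I ends protocol treatment and continues follow-up. Section 4.7 treats leaving treatment and leaving the study as different things.
3. **Whether a benefiting patient may stay.** 4.4.1 is unconditional at 3 weeks, while 4.3 allows an agreed exception. Sites could treat like patients differently, and a site that uses the exception would depart from 4.4.1 as written.

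What is at stake is patient safety and consistent handling across sites.

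**Working it through.** No formula applies and the plan gives no figure to reproduce. The check compares the texts row by row.

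**Step 1: Table I rows reached.** 4.4.1 pairs its platelet trigger (below 75,000) with recovery to below grade 2. Taking that pairing as given, its triggers reach three rows: neutrophils below 1.5, grade 2 platelets, and grade 3 or 4 platelets.

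| Situation | Held under 4.4.1 | Held under Table I | 3 weeks, 4.4.1 | 3 weeks, 4.3 general text | No recovery, Table I |
|---|---|---|---|---|---|
| Neutrophils <1.5 | topotecan | both | with G-CSF support: off study | withdraw unless PI, local PI and QAM agree | stop treatment; contact QAM and PI if benefiting (3 weeks) |
| Grade 2 platelets | topotecan | both | off treatment | same | stop treatment; contact QAM and PI if benefiting (3 weeks) |
| Grade 3/4 platelets | topotecan | both | off treatment | same | stop treatment; no contact line, no time limit in the row |

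**Step 2: the hold.** Table I interrupts both drugs in 3 of 3 rows; 4.4.1 names one drug in all of them. 4.4.1 does not say to continue pazopanib, so it is silent rather than contradictory. Holding both drugs satisfies every text.

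**Step 3: scope of removal.** 4.4.1 uses two terms: off study in its G-CSF sentence and off treatment in its platelet sentence. Table I consistently stops treatment and keeps follow-up.

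**Step 4: the exception.**
- The 4.3 clause covers any treatment-related toxicity, so it reaches 3 of 3 situations, including grade 3 or 4 platelets.
- The Table I contact instruction appears in 2 of 3 rows.
- 4.4.1 has an exception in 0 of 3.
- For neutropenia the mismatch is confined to patients given G-CSF, because 4.4.1 ties that removal sentence to G-CSF support.

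**Step 5: can a site comply with everything?** Suppose it removes the patient from treatment at 3 weeks and contacts the QAM and PI if the patient is benefiting. The removal requirement at 3 weeks is met. The 4.3 exception is not breached, because it is permissive and nobody has to agree to it. Table I is met, because its contact line comes after the instruction to stop. The open question is whether the discretionary exception is available in cases that 4.4.1 covers.

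**Step 6: reach.** Planned enrolment was 108 + 36 + 20 = 164. That is the number planned under the rules, not the number affected. The Amendment 13 entry in Appendix H says the study is closed to further accrual. The documents do not give the number still on treatment or the number with a cytopenia unresolved at 3 weeks, so no count is projected.

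**The case against.** The strongest reply is that nothing here is broken. All the texts stop treatment by default at 3 weeks. Section 4.4.1 is a G-CSF subsection under concomitant medications, while 4.3 is the toxicity section and already holds study treatment. A site would have to ignore 4.3 to keep giving pazopanib. On removal, 4.4.1 is the stricter rule, so following it adds no drug exposure. A stricter rule after G-CSF failure may also be a deliberate clinical choice.

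Much of this stands. A reader might infer that a site cannot obey both rules; Step 5 shows that it can. A reader might also take the Table I contact line as permission to continue. It implies a route but does not grant one, and the only explicit route is the clause in 4.3. The missing contact line in the grade 3 or 4 platelet row might suggest that no exception exists there, but the general 4.3 clause covers that group too. The point about clinical choice also stands: simply deleting the removal sentences would settle the G-CSF question without the sponsor. It would also drop the only platelet-specific 3-week limit for grade 3 or 4 thrombocytopenia.

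The reply does not dispose of the hold wording. A section that lists the same count thresholds and names one drug invites misreading, and 4.4.1 carries no pointer to the fuller rule. Nor does it explain removal from study. The general text of 4.3 also uses study-level wording, so the edit aligns 4.4.1 with Table I and 4.7 rather than with every sentence of 4.3.

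**Conclusion.** The point holds in limited form. Section 4.4.1 names one drug where Table I interrupts two (3 of 3 rows). It uses study-level removal where Table I ends treatment only. It is silent on an exception that 4.3 makes available in all 3 situations and that Table I points towards in 2. The first two are drafting faults worth correcting. The third is a question for the sponsor to answer.

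Two further inferences are not supported. Loss of follow-up is not shown: 4.6 sets follow-up after treatment ends, and 4.7 bars it only when consent is withdrawn. An effect on the primary endpoint might be inferred from 6.3, which can make a patient non-evaluable if removed from treatment before week 12 for reasons other than progression or death. But removal is the default under every text, and the documents show no patient whose evaluability turned on this wording. Cohort 1 was already closed to accrual at Amendment 10 (3.28.19), about 15 months before this version (06.26.20).

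The conclusion assumes that the exception clause in 4.3 applies to the 3-week recovery limit as well as to the longer interruption named in the same sentence. It also takes 4.4.1's own pairing of its platelet threshold with grade 2. The practical reach is patients still on treatment, a number that the documents do not give and that could be small or zero.

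**What to change.** In Section 4.4.1:

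1. Replace the hold and resume wording with: *Hold and restart both pazopanib and topotecan per 4.3 and Table I.* Keep the G-CSF permission as it is.
2. Replace removal from study with: *removed from protocol treatment, with follow-up per protocol.*
3. Keep the 3-week limit, including for grade 3 or 4 platelets.
4. Add one sentence, decided by the sponsor, saying whether the benefit exception in 4.3 applies after 3 weeks, including after failure of G-CSF support and for grade 3 or 4 platelets.

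The cost is a wording amendment to one section and one clinical decision. It needs no new data, visits or analyses.
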